1.4 Stereotactic body radiotherapy (SBRT) in pancreatic cancer

SBRT in pancreatic cancer shows great promise with initial studies showing high rates of local control. The initial study from Stanford escalated the dose of single fraction radiotherapy from 15 Gy in a single fraction to 25 Gy in a single fraction [3]. A subsequent phase II study treated patients to 45 Gy in 25 fractions with conventionally fractionated radiation, followed by 25 Gy in a single fraction [4]. Two of the 16 patients in this trial (13%) had grade 3 toxicity. Additional data with 25 Gy in a single fraction found

high rates of local tumor control with a 1-year freedom from local progression rate of 84% [5]. Unfortunately, the Stanford group found increased risk of late toxicity with the 25 Gy in 1 fraction regimen [6]. The close proximity of the stomach and duodenum put these organs at risk in radiotherapy directed at the pancreas. Of 73 patients treated with 25 Gy in a single fraction, 12 had grade 2-4 duodenal toxicity [6].

More recently, Stanford has preliminarily reported on a phase II trial 5-day course of SBRT [7]. This 5 fraction schedule going to 33 Gy was safe, with one reported toxicity event, though the efficacy was lower with decreased rates of local control. The observation that 33 Gy in 5 fractions was safe but had lower local control suggests that there may be room for dose escalation. This current trial will determine the maximal tolerated dose of SBRT in 5 fractions, for which the efficacy will be tested in a subsequent phase II trial.

This trial will escalate the dose from 40 Gy in 5 fractions, to 60 Gy in 5 fractions, at 5 Gy intervals. Comparing different radiation fractionation schedules is complex, though the standard metric used is the biologic effective doses (BED), and the BED of multiple radiation fractionation schedules is provided below in Table 1. The selection of a dose range with this study was based on a number of factors. First, the starting dose level of 45 Gy has been found safe in recently reported hypofractionated regimens in pancreatic cancer [8], in five fractions is the natural extension beyond 33 Gy in five fractions found safe by the Stanford researchers. The final dose level of 60 Gy in five translates into a BED of 132 for tumor response, and 300 for late toxicity. This final dose level is similar to that used by Koong, et al. with 141 for tumor response, and 305 for late toxicity.

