2.2 Secondary Aims

- 2.2.1 To estimate the rate of local tumor progression after SBRT.
- 2.2.2 To estimate the rate of distant disease progression after SBRT.
- 2.2.3 To measure overall survival after SBRT.
- 2.2.4 To estimate a dose-response between radiation dose and local control.
- 2.2.5 To measure longitudinal quality of life before and after SBRT.

- 2.2.6 To determine the correlation between quality of life, and disease progression after SBRT.
- 2.2.7 To determine if any dose-volume parameters predict grade ≥ 3 duodenal toxicity.
- 2.2.8 To determine if patients are able to receive additional chemotherapy after SBRT.
- 2.2.9 To identify natural anatomical surrogates that best correlate with the motion of the fiducial markers.
- 2.2.10 To determine if adaptive RT would be beneficial.

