12.1.2 Secondary Endpoints

12.1.2.1 Local control. The cumulative incidence of local failure will be determined for all patients treating distant progression or death as a competing

risk. Local progression will be defined as a $\geq 20\%$ increase in size on CT compared with CT prior to SBRT.

12.1.2.2 Distant metastatic progression rate. The cumulative incidence of distant metastatic failure will be determined for all patients treating death as a competing risk. In patients initially presenting with locally advanced disease, distant disease progression will be defined as the appearance of new metastatic lesions. In patients presenting with metastatic disease, distant progression will be defined as a $\geq 20\%$ increase in size on CT of the previously noted metastatic lesions.

12.1.2.3 Overall survival. Overall survival will be measured from the date of diagnosis through death of any cause. Survival will also be reported from the date of SBRT for comparisons to other trials in the literature. Finally, survival will be stratified by those with locally advanced disease, and those with metastatic disease on presentation.

12.1.2.4 Dose response. An exploratory analysis evaluating for a correlation between radiation dose response and local control will be done with a competing risk analysis, dividing patients into two groups stratified by the median dose..

12.1.2.5 Longitudinal quality of life. We will track longitudinal quality of life using the European Organization for Research and Treatment in Cancer (EORTC) quality of life core cancer questionnaire with the pancreatic cancer module (EORTC QLQ C-30/ PAN26) (see appendix). The questionnaire will be given prior to treatment, and periodically during follow-up visits after treatment has concluded. Trends will be assessed with a linear mixed effects model.

12.1.2.6 Correlation between quality of life and disease progression. Disease progression is a commonly used surrogate endpoint in clinical trial with pancreas cancer, however its relationship with quality of life has not clearly been demonstrated. Therefore, we will assess for correlation between quality of life and local or distant disease progression.

12.1.2.7 Dose-volume relationship with duodenal/gastric toxicity. We will plan to use logistic regression models to determine the relationship between grade ≥ 3 duodenal or gastric toxicity and dose to these structures. The dose to the duodenum will be extracted from our treatment planning system.

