12.2 Trial Design, Sample Size, and Study Duration

12.2.1 Trial Design: We will use a time to event continual reassessment method (TITE-CRM) trial design [11] to enroll a maximum of 30 patients onto this protocol.

The primary goal of this trial will be to determine the SBRT dose associated with a dose-limiting toxicity (DLT) in 20% of patients. DLT will be defined as grade ≥ 3 gastrointestinal toxicity (defined further below).

The TITE-CRM extends the original CRM by weighting each patient's contribution to the likelihood function described below. To determine the recommended dose for a newly enrolled patient, model parameters are estimated via the weighted likelihood. All previously enrolled patients who had either experienced toxicity or had completed the 12-month observation period without toxicity are assigned weights of 1; otherwise they are assigned weights equal to the proportion of the observation period they have completed.

The first patient in this study will enroll at dose level #2. Dose de-escalation can occur at anytime, though dose escalation will be restricted to 1 level between sequential patients. Additionally, before escalating the dose to the next level two conditions must be met: 1) the sum of the observation periods for all patients at the current dose level must be at least 12 months; and 2) at least one patient must have been under observation for at least 6 month at the current dose level. The rationale for these two conditions is mainly due to the short life expectancy of this patient population, which has a median survival of 8.25 months.

A two-parameter logistic regression model will be used to estimate the probability of toxicity at each dose level after each patient has been enrolled, which will inform the decision as to whether we should dose-escalate the patient in question. A final two-parameter logistic model will be fitted using follow-up data from 6 months after accrual of the last patient

Table 3. A priori toxicity estimation

Dose level	Probability of dose limiting toxicity
1	0.01
2	0.05
3	0.10
4	0.20
5	0.30

12.2.2 Dose Limiting Toxicity: The only toxicity observed thus far in pancreas SBRT has been related to nearby normal gastrointestinal organs, namely the duodenum and

stomach. Dose limiting toxicity in this study will be defined as any grade 3-5 gastrointestinal toxicity as measured by the Common Terminology for Adverse Events, version 4.0 (see appendix).

12.2.3 Maximum Sample Size: 30

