12.2.4 Study duration: We anticipate accruing 12 patients per year, and will follow the last patient for a minimum of 6 months.

12.2.5 Interim analysis: This TITE-CRM trial design will de-escalate the radiation dose rapidly according to the observed dose-limiting toxicity. In addition to this built-in dose de-escalation we plan to conduct interim safety analysis after enrollment of every patient. We will stop the trial early if either of the following three conditions are met:

Condition 1 for early trial stoppage: more than 50% of patients at any dose level experience a dose-limiting toxicity.

Condition 2 for early trial stoppage: more than 34% of patients at dose level #1 experience a dose-limiting toxicity.

12.2.6 Operating Characteristics of the design: We used simulation to investigate the operating characteristics of our TITE-CRM configuration. We set the prior probability of toxicity at dose levels as in the table above, and investigate four different scenarios for the true underlying probabilities of toxicity:

- Scenario 1: Toxicity probabilities (.01, .05, .10, .20, .30) for dose 1-5, respectively (Prior Probability = True Probability)
- Scenario 2: Toxicity probabilities (.01, .05, .07, .10, .15) for dose 1-5, respectively (Prior Probability > True Probability)
- Scenario 3: Toxicity probabilities (.01, .05, .07, .10, .25) for dose 1-5, respectively (Prior Probability > True Probability)
- Scenario 4: Toxicity probabilities (.05, .10, .20, .30, .50) for dose 1-5, respectively (Prior Probability < True Probability)

We set our target rate of toxicity at the MTD to be .20, and set a vague normal prior with mean 0 and variance 1.34 (9). When a simulated patient enters the study, they are assigned to the dose chosen by the 'titecrm' function in the R library **dfcrm** (10), following the rules for dose escalation above. The incoming patient experiences a toxicity with probability given by the true underlying rate of toxicity for their assigned dose level, with toxicity time occurring uniformly between 0 and 12 months. Potential drop out (i.e. death) times are drawn randomly (with replacement) from the literature [5]. We set the number of simulations for each scenario at 5000.

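### Aim 2.2.4 asks for a dose-response in local control, but the exploratory median split in 12.1.2.4 gives no effect per dose level and states neither the cut nor a tie rule

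*Combined protocol and SAP*

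**What the plan says.** Section 2.2 lists as aim 2.2.4: "To estimate a dose-response between radiation dose and local control". Section 12.1.2.4 describes the matching analysis as "An exploratory analysis evaluating for a correlation between radiation dose response and local control", to be done by competing-risk methods, "dividing patients into two groups stratified by the median dose". No other section plans an analysis of local control by dose level or by continuous dose.

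Dose is an ordered variable with equal steps. Section 1.4 states: "This trial will escalate the dose from 40 Gy in 5 fractions, to 60 Gy in 5 fractions, at 5 Gy intervals". The number of patients per level is not fixed. Section 12.2.1 uses a TITE-CRM design "to enroll a maximum of 30 patients onto this protocol". It adds that "The first patient in this study will enroll at dose level #2" and that "dose escalation will be restricted to 1 level between sequential patients".

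Section 12.1.2.4 gives no significance level, effect size, event count or power. It also does not define the median dose, assign patients treated at the median, or say what happens if one group is empty or very small.

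**The concern.** The aim and the method do not match. A two-group comparison can show an association, but it gives no change in local failure per 5 Gy. It treats the levels within each group as if they were the same dose.

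The split is also not fully defined. Adaptive allocation concentrates patients on a few levels, so many may sit exactly at the median. Moving them from one group to the other changes the comparison, and the choice could be made after outcomes are known.

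What is at stake is limited to aim 2.2.4. It still has some value: section 1.4 motivates escalation by the lower local control seen at 33 Gy, and this is the trial's only planned look at whether more dose improves local control.

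**Working it through.** **Plan's own figure.** There is none to reproduce, because 12.1.2.4 states no power or precision.

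**Inputs from the plan.** Five equally spaced levels, scored X = 1 to 5 (section 1.4, Table 1); at most 30 patients (12.2.1). The bar plot of average numbers per level in 12.2.6 was not readable in the copy used, so the allocations below are assumptions.

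**Step 1: information lost by the split.** Let Z = 1 for the upper group and p its share. If the log-hazard is linear in X, the efficiency of the split relative to a linear trend, for small effects, is

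r² = [E(XZ) − E(X)·p]² / [Var(X)·p(1−p)], and the loss is 1 − r².

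*Equal numbers, 6 per level, upper group above the median (levels 4–5).* E(X) = 3, Var(X) = 2, p = 0.4, E(XZ) = (4+5)/5 = 1.8. The covariance is 1.8 − 1.2 = 0.6, so r² = 0.36/(2 × 0.24) = 0.75. The loss is 25%, and 30 patients are worth 30 × 0.75 = 22.5 analysed by trend. Placing level 3 in the upper group gives the same value.

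*8/8/7/7 on levels 2–5.* E(X) = 103/30 = 3.433, Var(X) = 391/30 − 3.433² = 1.246, median = level 3.
- Above the median (14 patients): covariance 63/30 − 3.433 × 14/30 = 0.498; r² = 0.248/(1.246 × 0.249) = 0.80; loss 20%.
- At or above the median (22 patients): covariance 87/30 − 3.433 × 22/30 = 0.382; r² = 0.146/(1.246 × 0.196) = 0.60; loss 40%.

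*Two levels used equally.* Z and X carry the same information, so the loss is 0%.

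**Step 2: empty groups.** With 6/8/16 on levels 2–4, patients 15 and 16 in dose order are both at level 4. The median is level 4 and nobody is above it. With 16/8/6 on levels 2–4 the median is level 2. Under an at-or-above rule nobody is then in the lower group.

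**Step 3: simulated allocations (illustrative).** TITE-CRM allocations were simulated under the 12.2.1 escalation rules, the Table 3 prior probabilities and the 12.2.6 setting ("We set our target rate of toxicity at the MTD to be .20, and set a vague normal prior with mean 0 and variance 1.34"). Death times were assumed exponential with the stated median of 8.25 months. There were 2,000 runs for each of the four toxicity scenarios and each model and accrual variant.

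| Split rule | Mean loss | Empty group |
|---|---|---|
| Above median | 30–36% | upper, 2–11% of trials |
| At or above median | 23–28% | lower, 1.5–16% |
| Above level 3 (fixed) | 25–36% | upper, 8–16% (scenarios 1–3), 36–41% (scenario 4) |

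These runs did not match the Table 4 power in most scenarios (for scenario 2, 0.59–0.66 against 0.436). The plan's death times come from a cited source that was not available, and the model variant is not fully stated. The table therefore shows what can happen, not what the plan's own simulation would give, and it is not evidence that Table 4 is wrong.

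**Step 4: power (illustrative).** For D local failures, equal allocation, two-sided 0.05 and hazard ratio HR per level:
- Trend: Φ(√(2D)·|ln HR| − 1.96).
- Split: Φ(√(0.24D)·2.5·|ln HR| − 1.96), where 2.5 is the difference in mean level between the groups (4.5 − 2).

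With D = 10, HR 0.75 gives 0.25 by trend and 0.20 by split. HR 0.65 gives 0.49 and 0.39.

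A simulated cause-specific score test used 30 patients, assumed level shares .04/.29/.32/.25/.10, exponential deaths with median 8.25 months, 24 months' maximum follow-up, and a local-failure hazard of 0.06 per month at level 3 unless stated:

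| Assumed truth | Linear dose | Above median | At or above |
|---|---|---|---|
| HR 0.75 per level | 0.16 | 0.10–0.11 | 0.15–0.16 |
| HR 0.6 per level | 0.37–0.38 | 0.23–0.24 | 0.33–0.34 |
| HR 0.5 per level | 0.59–0.60 | 0.37–0.38 | 0.50 |
| HR 0.6, hazard 0.0145 per month | 0.14–0.15 | 0.05–0.06 | 0.16 |
| Step above level 3, HR 0.2 | 0.29–0.31 | 0.37 | 0.20 |

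Ranges cover repeated runs. The hazard of 0.0145 follows from the 84% one-year freedom from local progression in section 1.4: −ln(0.84)/12. It gives about 4 local failures, against about 12 in the first three rows. Distant progression was not modelled, although 12.1.2.1 also counts it as a competing event, so event counts are if anything too high.

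**The case against.** The strongest reply is that nothing in the trial depends on this analysis. It is labelled exploratory, has no error rate or decision attached, and section 1.4 leaves efficacy to a later phase II trial. That stands, and it limits the weight of the point.

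Second, 12.1.2.4 speaks of a correlation, and a two-group comparison does address association. That is fair for the text of 12.1.2.4. It does not meet aim 2.2.4, which asks for an estimate of dose-response.

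Third, r² measures efficiency only if the log-hazard is linear in dose. If the truth is a step and the cut falls on it, the split wins (0.37 against about 0.30 above). This stands, but the plan gives no reason to expect a step at the median. The tumour BED values in Table 1 (72, 86, 100, 116, 132) are nearly evenly spaced, so a linear score is a natural default.

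Fourth, the larger power gains need strong effects. HR 0.6 per level is 0.6⁴ = 0.13 across the range, and 0.5 is 0.06. At HR 0.75, or with about 4 events, the advantage over an at-or-above split disappears. This also stands.

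A reader might infer that the split discards a fixed share of the information, such as 30%. The documents give no such figure, and the loss runs from 0% to 40% in the worked allocations. A reader might also infer that the upper group in particular will be empty. That holds only under some readings of the cut. Under an at-or-above rule it is the lower group that can be empty.

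**Conclusion.** The point holds as a mismatch between aim and method, together with an undefined split. The planned analysis gives no effect per dose level, and neither the cut nor the tie rule is stated although allocation is adaptive.

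Given a log-linear dose effect, the loss is 25% with equal numbers per level and about 20–40% in illustrative allocations, depending on the tie rule. It is zero if only two levels are used equally. One group can be empty.

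The power figures rest on assumed allocations, hazards and effect sizes, and only illustrate the size of the gain. For weak to moderate effects the sample size is the main limit, whichever coding is used. The documents do not support reading this as a threat to the MTD, dose assignment or any trial decision. It is a cheap improvement to a minor exploratory secondary aim.

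**What to change.** In 12.1.2.4, make the main analysis a competing-risk regression of local failure with dose as a single ordered or continuous covariate. State whether the hazard ratio is cause-specific or subdistribution, and report it per 5 Gy with its 95% CI. Keep the exploratory label.

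Two-group cumulative incidence curves may stay as a display. If so, state in advance whether the cut is the median dose received or a fixed level, which group takes patients at the cut, and what is shown if a group is empty or very small.

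The cost is one or two sentences, with no extra data or patients. The small downside is the assumed log-linear dose effect, which would be less efficient than a well-placed split if the true relation were a step.

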Operating characteristics of the TITE-CRM simulation under different scenarios are included in the table below. 'Power' is defined as the simulated probability that the algorithm will recommend the correct MTD, defined in our simulation as the dose whose true toxicity probability is closest to, but not greater than, the target (dose 4, 5, 4, and 3 for each of the four scenarios, respectively) at the trials conclusion. Trial duration is the amount of time (in months) from the first patients' enrollment to the end of the final patients observation period. Total Obs. is the cumulative observation time (in months) on all 30 patients. Pr(Tox.) is the simulated probability of toxicity in that configuration, and Pr(Tox. Above MTD) is the simulated probability of a subject having toxicity at a dose above the MTD.

Table 4. Operating characteristics

[figure not shown]
	‘Power’	Trial Duration	Total Obs.	Time	Pr(Tox.)	Pr(Tox. Above MTD)
Scenario 1	0.341	39.4	237.0		0.091	0.016
Scenario 2	0.436	39.4	240.5		0.062	0.014
Scenario 3	0.369	39.5	239.1		0.071	0.022
Scenario 4	0.334	39.5	233.9		0.116	0.029

The probability of recommending each dose as the MTD by scenario is included in the table below.

[figure not shown]
Table 5. Probability of recommending each dose as the MTD

	Dose 1	Dose 2	Dose 3	Dose 4	Dose 5	MTD and (MTD - 1)
Scenario 1	0.000	0.123	0.386	0.341	0.150	0.727
Scenario 2	0.001	0.068	0.195	0.299	0.436	0.736
Scenario 3	0.003	0.069	0.204	0.369	0.356	0.573
Scenario 4	0.062	0.500	0.334	0.094	0.011	0.834

A boxplot of the number of patients treated above the MTD (treated above dose 4, 4, and 3, respectively) in scenarios 1, 3 and 4 is below.

A barplot of the average number of patients treated at each dose level with each scenario is below.

REFERENCES

1. Siegel R, Naishadham D Jemal A. Cancer statistics, 2013. *CA Cancer J Clin* 2013;63:11-30.

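### Section 12.1.2.7 plans logistic regression for an outcome with about 2 to 4 expected events, where maximum-likelihood odds ratios are unstable; a penalised fit on pre-named metrics would be better

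*Combined protocol and SAP*

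**What the plan says.** Aim 2.2.7 is "To determine if any dose-volume parameters predict grade" 3 or higher duodenal toxicity. Section 12.1.2.7 widens the outcome to "duodenal or gastric toxicity and dose to these structures" and gives the method: "We will plan to use logistic regression models to determine the relationship between grade" 3 or higher toxicity and dose. On data it adds only "The dose to the duodenum will be extracted from our treatment planning system"; stomach dose is not mentioned.

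No candidate metric, number of predictors per model, small-sample or penalised estimator, interval method or minimum event count is stated. Section 12.1.2.4 (dose response) is labelled exploratory; 12.1.2.7 is not.

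The size of the data set follows from section 12.2. The trial plans "to enroll a maximum of 30 patients onto this protocol", and "Dose limiting toxicity in this study will be defined as any grade 3-5 gastrointestinal toxicity". In 12.2.6, "Pr(Tox.) is the simulated probability of toxicity in that configuration", and Table 4 gives 0.091, 0.062, 0.071 and 0.116 for Scenarios 1 to 4.

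**The concern.** Logistic regression draws its information mainly from the rarer outcome. If only a handful of patients have an event, the usual maximum-likelihood fit has a long upper tail when a real association exists, and Wald intervals behave poorly. With no events it cannot be fitted at all. The plan neither acknowledges the expected count nor says what will be done when it is very low.

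At stake is how far the reported dose-volume association can be trusted. A single published odds ratio from this analysis could be much too large, and a reader could not tell that from the Wald interval. The MTD, dose assignment and stopping rules do not depend on it.

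**Working it through.** **Inputs.** Maximum N = 30 (12.2.1 and 12.2.3). Pr(Tox.) from Table 4. DLT covers all grade 3-5 gastrointestinal toxicity (12.2.2); Appendix IV includes colonic, ileal, pancreatic and biliary terms.

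**Step 1: is Table 4 a fair basis?** A TITE-CRM simulation was run with the stated prior toxicities, target, N(0, 1.34) prior, start level and escalation rules, and 12-month uniform toxicity times. It assumed a one-parameter power model and exponential dropout, because the dropout data are not in the documents. Pr(Tox.) for Scenarios 1 to 4 was 0.078, 0.050, 0.058 and 0.108 with median dropout at 8.25 months. With a median of 11.4 months it was 0.089, 0.057, 0.068 and 0.123. All are within 2 percentage points of Table 4. The Table 5 selection probabilities were not matched, but nothing here uses them.

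**Step 2: expected events.** Expected DLTs = 30 x Pr(Tox.):

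| Scenario | Expected | P(0) | P(0 or 1) | P(2 to 4) | P(5 or more) | 95% range |
|---|---|---|---|---|---|---|
| 1 | 30 x 0.091 = 2.73 | 0.06 | 0.23 | 0.64 | 0.13 | 0-6 |
| 2 | 30 x 0.062 = 1.86 | 0.15 | 0.44 | 0.53 | 0.04 | 0-5 |
| 3 | 30 x 0.071 = 2.13 | 0.11 | 0.36 | 0.58 | 0.06 | 0-5 |
| 4 | 30 x 0.116 = 3.48 | 0.03 | 0.12 | 0.61 | 0.26 | 1-7 |

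The probabilities are binomial with n = 30. For Scenario 2, P(0) = 0.938^30 = 0.147 and P(1) = 30 x 0.062 x 0.938^29 = 0.290, which sum to 0.437. Duodenal plus gastric events are a subset of DLTs, so these are upper limits for their expected count, provided they are counted over the same 12 months and on the same grading scale.

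**Step 3: behaviour of the estimator at the Table 4 rates.** Assumptions: 30 patients, one standard-normal metric, true log odds ratio 0.7 per SD, about 3000 data sets per rate, event rates spanning 0.062 to 0.116. Ranges cover repeated runs.

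- Mean maximum-likelihood log odds ratio, where finite: 0.84 to 0.99. Excess: 0.84/0.7 = 1.20 to 0.99/0.7 = 1.41, so about 20-40%.
- Median maximum-likelihood estimate: 0.72 to 0.75.
- Root mean squared error: 1.2 to 1.8 for maximum likelihood, 0.76 to 0.87 for Firth. Ratios: 1.2/0.76 = 1.6 and 1.8/0.87 = 2.1.
- Firth mean 0.66 to 0.72; Firth median about 0.6.
- No finite estimate: about 5-19% of all trials, but only about 1% (0.6 to 1.4%) of trials with at least 2 events.
- With a true log odds ratio of 0, the nominal 5% Wald test rejected in 0.4 to 1.8% of trials, and the estimate was centred near 0.

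**Step 4: fixed event counts.** With the count held fixed, mean log odds ratios were:

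| Events | True 0.693: ML | Firth | True 1.099: ML | Firth |
|---|---|---|---|---|
| 2 | 1.033 | 0.726 | 1.568 | 1.075 |
| 3 | 0.946 | 0.717 | 1.564 | 1.127 |
| 4 | 0.963 | 0.735 | 1.449 | 1.114 |
| 6 | 0.861 | 0.714 | 1.346 | 1.082 |

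At 2 to 4 events the maximum-likelihood excess runs from 1.449/1.099 = 1.32 to 1.033/0.693 = 1.49. Wald 95% limits lie a factor of 3.5 to 6.5 either side of the estimate. The 6-event row is what would be expected if every patient were at the target of "dose-limiting toxicity (DLT) in 20% of patients" (30 x 0.20 = 6). The mean is still 0.861/0.693 = 1.24 times the truth.

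**The case against.** The strongest case against is that this is one of ten secondary aims in a small phase I trial, and that the shortage is of information, which no estimator supplies. That stands in part. Firth estimates still had an SD of 0.74 to 0.86 around a true 0.70, and maximum-likelihood Wald power was only 2-10%. The plan's wording also does not exclude a penalised logistic model. But it does not specify one either, and on the same data the penalised fit removes most of the mean bias and cuts the root mean squared error to roughly half to two thirds.

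Four stronger readings are tempting and should be resisted.

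- *The trial will have 2 to 4 events.* That is a rounded expectation under four assumed scenarios. The chance of 2 to 4 is only 0.53 to 0.64.
- *The odds ratios will mostly be inflated or not estimable.* The typical (median) estimate is close to the truth, and the excess in the mean comes from the tail. There is no inflation when there is no effect. Failure to estimate comes mainly from trials with 0 or 1 event. With 0 events no method helps.
- *Looking at any parameter will add many chance findings.* Independent tests at a true 5% would give 22.6% for 5 metrics and 40.1% for 10, but the number of metrics is not in the documents, dose-volume metrics are correlated, and the Wald test here rejects far less often than 5%. The wording of aim 2.2.7 is an ordinary question, not a stated screening procedure.
- *Wrong dose-volume thresholds will go into the next trial.* Section 1.4 carries only the maximum tolerated dose forward to phase II.

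**Conclusion.** The concern holds as a question of estimator and specification. The method as written will probably be applied to about 2 to 4 events or fewer. If an association of the assumed size exists, the maximum-likelihood log odds ratio is then about 20-40% too large on average, with 1.6 to 2 times the root mean squared error of a Firth fit, and its Wald intervals are unreliable. Outright failure is about 1% once there are at least 2 events.

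These sizes rest on Table 4's scenarios, one roughly normal metric per model and a log odds ratio of 0.7 per SD; a bounded or skewed metric would give other figures. The upper-limit argument also assumes a common window and scale. Section 12.1.2.7 states neither, and 10.2 changes the grading scale for events after 90 days.

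The importance is minor to moderate: it improves a secondary analysis and leaves the MTD untouched.

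**What to change.** In 12.1.2.7:

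1. State the expected event count, and specify Firth-penalised logistic regression with profile penalised-likelihood intervals, one predictor per model.
2. Name in advance one main metric per organ on an absolute dose scale. Volume above the prescription dose would be a poor choice: 6.1.1.5 limits it to 1 cm³, the prescription runs from 40 to 60 Gy across cohorts, and 6.1.1.5 allows the PTV prescription to be reduced, so the same value would mean different physical doses.
3. Extract stomach dose as well as duodenal dose, and align aim 2.2.7 with the outcome in 12.1.2.7.
4. With fewer than 2 events, fit no model and only list the metric for patients with and without events.
5. Label the analysis exploratory, as in 12.1.2.4, and report how many metrics were examined.

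The cost is a few sentences of SAP wording and standard software, with no new patients or visits. The stomach is already a constrained organ in 6.1.1.5, so its dose should be obtainable from the same plans. The statistical price is slight shrinkage of the typical estimate (median about 0.6 against a true 0.7). Intervals will remain wide and should be reported as such.
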